1. EXECUTIVE SUMMARY

Title:	Study of Clinical Efficacy of Antimicrobial Therapy Strategy Using Pragmatic Design in Idiopathic Pulmonary Fibrosis (CleanUP-IPF)
Location:	Approximately 30-40 clinical sites in the United States
Objectives:	To compare the impact of an antimicrobial therapy strategy on clinical outcomes (hospitalization or death)
Study Design:	500-patient, randomized, un-blinded, phase III, multicenter clinical trial of an antimicrobial therapy strategy in idiopathic pulmonary fibrosis patients
Treatment Regimens:	
1:1 randomization to either oral antibiotic (co-trimoxazole or doxycycline) in addition to standard-of-care or standard-of-care alone.
 
The subject randomized to antimicrobial therapy will be treated with trimethoprim 160mg/800mg sulfamethoxazole (double strength co-trimoxazole) twice a day plus folic acid 5 mg daily unless there is a contraindication to this therapy.
 
If the subject develops an intolerance to co-trimoxazole the dosage can be decreased to once a day 160mg trimethoprim/800mg sulfamethoxazole (one double strength co-trimoxazole) three times weekly plus folic acid 5 mg daily.
 
If intolerance continues with co-trimoxazole then the antimicrobial agent can be changed to doxycycline (without folic acid).
 
Subjects with a contraindication to co-trimoxazole will be treated with doxycycline (without folic acid). Doxycycline will be dosed at 100 mg once daily if body weight is < 50 kg and 100 mg twice daily if \geq 50 kg.

Primary Endpoint:	Time to first non-elective, respiratory hospitalization or all-cause mortality
Secondary Endpoints:	
 • Time to death from any cause • Time to first non-elective, respiratory hospitalization • Time to first non-elective, all-cause hospitalization • Total number of non-elective respiratory hospitalizations • Total number of non-elective all-cause hospitalizations • Change in FVC from randomization to 12 months

[figure not shown]
	
• Change in DLCO from randomization to 12 months• Total respiratory infections• Change in UCSD-Shortness of Breath Questionnaire and Fatigue Severity Scale score from randomization to 12 months• Change in Leicester Cough Questionnaire score from randomization to 12 months• Change in EQ-5D score and SF-12 score from randomization to 12 months• Change in ICEpop CAPability measure for Older people (ICECAP-O) score from randomization to 12 months
--	---

Overview of the Pulmonary Trials Cooperative and the CleanUP-IPF study

The CleanUP-IPF trial is a collaborative effort involving the following groups:

1. National Institutes of Health
2. National Heart, Lung, and Blood Institute
3. University of Pittsburgh
4. Weill Cornell University
5. Duke Clinical Research Institute
6. Clinical Sites

The CleanUP-IPF leadership team shall be referred to as the “CleanUP-IPF Protocol Leadership Group” (PLG). The CleanUP-IPF PLG is one of multiple PLGs which comprise the Pulmonary Trials Cooperative (PTC). The following flow chart depicts each group which makes up the PTC:

Organizational Components

- Protocol Leadership Groups (PLGs) – design and carry out clinical studies
- Network Management Core (NEMO) – facilitate the research conducted by the PTC
- Operations Committee – primary responsibility for the implementation, oversight, and continuing evaluation of PTC studies
- Executive Committee – provide leadership and oversight to the PTC at large
- Clinical Sites – recruit and enroll participants, deliver the study intervention, complete clinic visits and phone calls, collect and enter data, and carry out procedures as defined by each study’s protocol

- Data and Safety Monitoring Board (DSMB) – review the design of each study, monitor patient safety, and review progress
- NHLBI Project Office – oversight for the whole endeavor

More information about the PTC and CleanUP-IPF can be found at ...

<http://www.pulmonarytrials.org/>

<https://clinicaltrials.gov/ct2/show/NCT02759120>

2. HYPOTHESES AND OBJECTIVES

2.1 Primary Objective and Hypothesis

The **primary objective** of the **CleanUP-IPF** study is to compare the effect of standard care vs. standard care plus antimicrobial therapy (co-trimoxazole or doxycycline) on clinical outcomes in patients diagnosed with idiopathic pulmonary fibrosis.

Our **overall hypothesis** is that reducing harmful microbial impact with antimicrobial therapy will reduce the risk of non-elective, respiratory hospitalization or death in patients with IPF.

2.2 Secondary Objectives

Secondary objectives of this protocol will be to examine the effect of this treatment strategy for the following endpoints:

- Time to death from any cause
- Time to first non-elective, respiratory hospitalization
- Time to first non-elective, all-cause hospitalization
- Total number of non-elective respiratory hospitalizations
- Total number of non-elective all-cause hospitalizations
- Change in FVC from randomization to 12 months
- Change in DLCO from randomization to 12 months
- Total number of respiratory infections
- Change in UCSD-Shortness of Breath Questionnaire from randomization to 12 months
- Change in Fatigue Severity Scale score from randomization to 12 months
- Change in Leicester Cough Questionnaire score from randomization to 12 months
- Change in EQ-5D score and SF-12 score from randomization to 12 months
- Change in ICEpop CAPability measure for Older people (ICECAP-O) score from randomization to 12 months

3. BACKGROUND AND RATIONALE

Idiopathic pulmonary fibrosis (IPF), a fibrotic interstitial lung disease characterized by the histopathologic pattern of usual interstitial pneumonia (UIP), has a median survival of 3-5 years' post-diagnosis but exhibits heterogeneous longitudinal disease progression. Recent studies of pirfenidone and nintedanib confirm beneficial effects on longitudinal change in forced vital capacity but inconsistent benefits on clinical endpoints or health status. Both of these agents can be difficult to tolerate and are expensive.

A recent study showed that an abnormal lung microbial community is independently associated with disease progression in IPF subjects (COMET)¹; this has been confirmed by a second investigative group². Similarly, it has been demonstrated that polymorphisms in the TOLLIP gene are associated with impaired outcome in IPF patients³. Additional preliminary data suggest that a systemic marker of inflammatory cell activation is associated with IPF disease progression⁴. Lastly, preliminary data from COMET suggest that a circulating gene expression signature of altered host response is associated with the aberrant lung microbial community. Intriguingly, other investigative groups have suggested improved clinical outcomes in IPF patients treated with co-trimoxazole or doxycycline compared to matched placebo⁵⁻⁷. The totality of these data suggests that an abnormal lung microbiome interacting with genetic susceptibility in host response may be associated with impaired clinical outcomes in IPF.

Our principal hypothesis is that antimicrobial therapy in IPF patients will improve clinical outcomes in a pragmatic therapeutic trial. The study aims are:

Aim 1. To determine if antimicrobial therapy (co-trimoxazole or doxycycline) in addition to standard care compared to standard care alone improves the time to non-elective respiratory hospitalization or death.

Aim 2. To determine if response to antimicrobial therapy is a function of genetic susceptibility to impaired host response in IPF patients.

We propose to examine the potential of precision medicine by examining the interaction of antimicrobial therapy with baseline genotype. Our long-term goal is to define patient-specific therapy in IPF.

4. STUDY POPULATION AND ELIGIBILITY CRITERIA

4.1 Inclusion Criteria

1. ≥ 40 years of age
2. Diagnosed with IPF by enrolling investigator
3. Signed informed consent

4.2 Exclusion Criteria

1. Received antimicrobial therapy in the past 30 days for treatment purposes (antibiotic prophylaxis for procedures do not meet criteria, nor do antivirals)
2. Contraindicated for antibiotic therapy, including but not exclusive to:
 - a. Allergy or intolerance to BOTH tetracyclines AND trimethoprim, sulfonamides or their combination
 - b. Allergy or intolerance to tetracyclines AND known potassium level > 5 mEq/L in the past 90 days.
 - i. If the enrolling physician feels the potassium level has normalized, documentation to that effect must be provided.
 - c. Allergy or intolerance to tetracyclines AND concomitant use of angiotensin converting enzyme inhibitor (ACEI), angiotensin receptor blocker (ARB), potassium sparing diuretic, dofetilide, methotrexate, azathioprine, mycophenolate mofetil, cyclophosphamide
 - d. Allergy or intolerance to tetracyclines AND known glucose-6-phosphate dehydrogenase deficiency
 - e. Allergy or intolerance to tetracyclines AND untreated folate or B12 deficiency
 - f. Allergy or intolerance to tetracyclines AND known renal insufficiency (defined as a GFR < 30 ml/min within the previous 90 days)
 - i. If the enrolling physician feels the renal dysfunction has resolved, documentation to that effect must be provided.
 - g. Seizure disorder on antiepileptic therapy.
3. Pregnant (as determined by urine dipstick pregnancy test at randomization), or anticipate becoming pregnant
4. Use of an investigational study agent for IPF therapy within the past 30 days, or an IV infusion with a half-life of four (4) weeks
5. Concomitant immunosuppression with azathioprine, mycophenolate, cyclophosphamide, or cyclosporine.

Participation in other IPF clinical trials or registries, while participating in the CleanUP-IPF trial, is not exclusionary assuming the participant meets all other eligibility criteria.

5. TREATMENT INTERVENTIONS

This will be an unblinded, randomized clinical trial comparing the following treatment strategies

- Standard care
- Standard care + oral antimicrobial therapy

Patients randomized to receive antimicrobial therapy will receive a prescription drug voucher for the medication (and folic acid if given co-trimoxazole) during the enrollment visit. To minimize risk to the participating subject and to maximize a positive outcome we have created an algorithm for antimicrobial therapy that encourages use of co-trimoxazole but allows doxycycline use.

[figure not shown]
Figure 1 illustrates the proposed antimicrobial therapy algorithm. Contraindications to co-trimoxazole at enrollment include:

- allergy to sulfa products or trimethoprim
- renal insufficiency (GFR < 30 mL/min, defined as estimated from the blood urea nitrogen and creatinine)
- hyperkalemic (potassium > 5 mEq/L)
- concomitantly taking an ACEI, ARB, potassium sparing diuretic, dofetilide, methotrexate, azathioprine, mycophenolate mofetil, cyclophosphamide
- Other contraindication to co-trimoxazole in the investigator's opinion

Subjects meeting any of the above and randomized to antibiotic therapy will take doxycycline instead. Subjects on vitamin A or retinoids will need to stop these medications if randomized to doxycycline.

Co-trimoxazole intolerance is defined by the investigator. Mild intolerance (e.g. nausea, abdominal pain, headaches, anorexia) may require a dose adjustment to half dose. Moderate intolerance (e.g. decreased leukocytes, mild increase in potassium) require a dose adjustment or a switch to doxycycline at the investigator's discretion. A significant intolerance (e.g. leukopenia, hyperkalemia, decrease in GFR by more than 50% or to less than 30 ml/min, rash) requires stopping the co-trimoxazole and providing medical treatment as appropriate. Doxycycline should be started when medically appropriate in the opinion of the investigator after moderate or significant intolerance. All dose adjustments will be at the discretion of the treating physician(s) with the medical monitor available for consultation if needed. Dosing adjustments, and/or switching of co-trimoxazole to doxycycline, will be documented within the eCRFs, as well as the reason for the adjustment.

Figure 1

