5.3 Patient Safety and Concomitant Therapies

This study will evaluate and compare treatment strategies of standard care and standard care + antimicrobial therapy in patients with IPF.

Although investigators are encouraged to follow the assigned treatment strategy for the study duration, in all cases the patient’s safety based on the clinical judgment of the treating physician will take priority over the specific treatment assignment.

There is the potential of adverse cardiovascular events secondary to co-trimoxazole therapy; this is felt to possibly reflect a drug interaction with trimethoprim resulting in hyperkalemia^{8,9}. Review of older literature suggests that the major risk factors for trimethoprim related hyperkalemia are higher trimethoprim dose and renal insufficiency with hypoaldosteronism, and potassium altering medications and age as probable risk factors¹⁰. Our inclusion/exclusion criteria should mitigate this risk as will monitoring for hyperkalemia early after the introduction of co-trimoxazole therapy¹⁰.

If a subject randomized to the antimicrobial strategy group develops an intolerance to co-trimoxazole the dosage should first be decreased to one double strength 160mg trimethoprim/800mg sulfamethoxazole (co-trimoxazole) three times weekly plus folic acid 5 mg daily. If intolerance continues with co-trimoxazole then the antimicrobial agent can be changed to doxycycline (with no 5mg folic acid).

Doxycycline will be dosed at 100 mg once daily if body weight is < 50 kg and 100 mg twice daily if \geq 50 kg, and no 5mg folic acid will be prescribed.

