8. FOLLOW UP EVALUATIONS

All study participants will continue to be followed on a usual care basis. Refer to the schedule of assessments for more details. Study participants will be followed for up to a maximum of 36 months. It is anticipated that the overall study will end once the final enrolled patient completes their 12-month visit. Subjects randomized to antimicrobial therapy will remain on the assigned therapy until the end of the study or their 36-month study visit. Study participants are encouraged to contact their treating pulmonologist regarding their use of anti-microbial therapy after their study participation has ended. At the completion of the 36-month phone contact data collection will cease. To gain a better understanding of the long-term consequences of treatment, patients may be contacted up to 5 years after the end of their study participation. The primary analyses will be based on data collected until the end of the active treatment portion of the study.

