Concomitant Medication Review	X										
Concomitant Medication Update			X			X	X	X	X	X	X

Complete Blood Count (CBC)	X (if not available in last 90 days)			X ³	X ³		X ³		X ³		
Chemistry panel w/liver function tests	X (if not available in last 90 days)			X ³	X ³		X ³		X ³		
Electrolytes only		X ²									
Genotype	X										
Gene expression	X						X		X		
Buccal Swab, Fecal samples	X						X		X		
Patient Reported Outcomes Questionnaires ¹	X						X		X		
Clinical Events			X			X	X	X	X	X	X
Mortality			X			X	X	X	X	X	X
Hospitalization			X			X	X	X	X	X	X
Resp. infection			X			X	X	X	X	X	X

1. Patient reported questionnaires include: UCSD-SoBQ, Fatigue Severity Scale, Leicester Cough, EQ-5D, SF-12, ICECAP-O
2. For subjects receiving co-trimoxazole, a blood sample to document electrolytes will be drawn at week 1, Visit 1A.
3. For subjects assigned to the antimicrobial therapy arm, a blood sample to document complete blood count, liver function tests, and chemistry panel, will be drawn at 3 months, 6 months, 12 months, and 24 months to be obtained at Visit 2A, Visit 2B, Visit 4, and Visit 6, respectively.

16. APPENDIX B – CleanUP-IPF Laboratory Schedule

Antimicrobial Arm (Co-trimoxazole and Doxycycline Arms)

	CBC	Electrolytes	Chemistry plus liver function tests	Gene expression	Genotype	Buccal sample	Fecal sample	Approx. total Blood Amount
Baseline	x		x	x	x	x	x	28.5 ml
Week 1		x*						6 ml
3 month	x		x					8.5 ml
6 month	x		x					8.5 ml
12 month	x		x	x		x	x	18.5 ml
24 month	x		x	x		x	x	18.5 ml
*only in co-trimoxazole treated patients								88.5 ml

Standard of Care Arm

	CBC	Chemistry plus liver function tests	Gene expression	Genotype	Buccal sample	Fecal sample	Approx. total Blood Amount
Baseline	x	x	x	x	x	x	28.5 ml
12 month			x		x	x	10 ml
24 month			x		x	x	10 ml
							48.5 ml

Safety Labs

Complete Blood Count (CBC): WBC, RBC, hemoglobin, hematocrit, mean corpuscular volume (MCV), Platelets, mean platelet volume (MPV)

Electrolytes: Sodium, Potassium, Chloride, Carbon Dioxide (CO₂)

Chemistry: Sodium, Potassium, Chloride, Carbon Dioxide (CO₂), Urea Nitrogen (BUN) and Creatinine

Liver Function Studies: Alkaline Phosphatase, Total Bilirubin, Direct bilirubin, Aspartate Aminotransferase (AST), and Alanine Aminotransferase (ALT)

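### The drug contraindications to co-trimoxazole are tied to enrollment, and little in the visible text prompts a switch or a potassium check when a patient on co-trimoxazole later starts an ACEI, ARB or potassium-sparing diuretic

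*Protocol*

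**What the plan says.** Section 5 of the protocol gives the drug list under the words "Contraindications to co-trimoxazole at enrollment include". It names ACE inhibitors, ARBs, potassium-sparing diuretics, dofetilide, methotrexate, azathioprine, mycophenolate and cyclophosphamide. A patient on any of these who is randomized to antimicrobial therapy takes doxycycline. The on-therapy rules that follow in Section 5 (reduce, switch or stop) respond to observed intolerance, such as a potassium rise, hyperkalemia, a fall in GFR or a rash.

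Section 5.3 discusses hyperkalemia from trimethoprim and possible cardiovascular events. It counts "potassium altering medications and age as probable risk factors". For mitigation it says: "Our inclusion/exclusion criteria should mitigate this risk as will monitoring for hyperkalemia early after the introduction of co-trimoxazole" therapy. It also says that the patient's "safety based on the clinical judgment of the treating physician will take priority over the specific treatment assignment".

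On duration, Section 8 states: "Subjects randomized to antimicrobial therapy will remain on the assigned therapy until the end of the study or their 36-month study visit". On laboratory tests, Appendix A adds to the week-1 electrolytes (co-trimoxazole patients only) that the blood count, liver tests "and chemistry panel, will be drawn at 3 months, 6 months, 12 months, and 24 months". Appendix A also has a row headed "Concomitant Medication Update", marked at months 1, 6, 12, 18, 24, 30 and 36, with no action attached.

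Two places speak of contraindications without naming a time. The Executive Summary directs patients with a contraindication to doxycycline. SAP Section I does the same for patients taking an ACE inhibitor, an ARB or a potassium-sparing diuretic.

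**The concern.** The protocol treats co-trimoxazole with a listed drug as a combination to avoid. Exclusion criterion 2c goes as far as keeping out a tetracycline-intolerant patient who takes one, so at entry the sponsor would rather lose the patient than give the combination. A patient who starts the same drug during treatment has no matching explicit instruction.

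The two mitigations in Section 5.3 do not reach that patient. Entry criteria act once, and early monitoring is anchored to the start of co-trimoxazole, not to the start of the second drug. The rule to stop for hyperkalemia needs a potassium result, and nothing about the new drug prompts one. What is at stake is patient safety, on a risk that the protocol itself names.

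**Working it through.** No power or alpha figure is involved. The check is a reading of the schedule.

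**Inputs.** Draws that include potassium, for a patient on co-trimoxazole after baseline: week 1, months 3, 6, 12 and 24 (Sections 8.1, 8.3, 8.4, 8.6 and 8.8; Appendix A footnotes 2 and 3; Appendix B). Medication-update contacts from month 6: months 6, 12, 18, 24, 30 and 36 (Appendix A). Therapy: up to month 36 (Section 8).

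**Is the list of draws complete?** The Appendix B volumes for the antimicrobial arm sum to 28.5 + 6 + 8.5 + 8.5 + 18.5 + 18.5 = 88.5 ml, which is the stated total. No further draw is planned.

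**Gaps between draws.**
- Week 1 (7/30.44 = 0.23 months) to month 3: 2.8 months
- Months 3 to 6: 3 months
- Months 6 to 12: 6 months
- Months 12 to 24: 12 months
- Months 24 to 36: no draw, so up to 12 months of therapy

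If the month-12 visit falls 4 weeks early and the month-24 visit 4 weeks late, the longest gap is 12 + 56/30.44 = 13.8 months. That needs both visits at opposite ends of their windows.

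**Example.** An ACE inhibitor is started at month 14. Next scheduled potassium: 24 − 14 = 10 months. Next medication update: 18 − 14 = 4 months.

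**What a flag on the medication update would add after month 6.**

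| Listed drug started in months | Next draw | Next update | Earlier usable prompt from the flag? |
|---|---|---|---|
| 6–12 | 12 | 12 | No |
| 12–18 | 24 | 18 | Yes, 6 months earlier |
| 18–24 | 24 | 24 | No |
| 24–30 | none | 30 | Yes |
| 30–36 | none | 36 | No; study therapy ends at that contact |

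The flag therefore helps in two of the five periods, and even there it can come up to 6 months after the drug was started.

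**Who can reach the late gap.** Section 11.3 plans 30 months of enrollment and at least 12 months of follow-up. A patient enrolled at calendar month t has 42 − t months available, capped at 36. More than 24 months requires t below 42 − 24 = 18, so the period after month 24 concerns patients enrolled in the first 18 months.

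**The case against.** The strongest objection is that the rule may already exist. Section 5 refers to a therapy algorithm in Figure 1, which cannot be seen, and a switch rule would sit naturally there. Its absence from the visible text does not show that it is absent from the plan. This stands, and the point is conditional on it. Figure 1 does not, however, alter the laboratory schedule or attach an action to the medication-update row in Appendix A.

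A second objection is that visible text already supports a switch. The Executive Summary and SAP Section I are not limited to enrollment, Section 5.3 puts safety above assignment, and Section 5 leaves dosing to the treating physician with a medical monitor available. In a pragmatic, unblinded trial that discretion is deliberate. This too stands in part. It rules out the reading that the plan offers no protection, or that patients would in fact go 12 months without a potassium test; follow-up is on a usual-care basis and routine tests may fill part of the gap. But none of this text names a newly started drug as the trigger, sets a time or asks for a potassium test. It works only once someone notices the new drug. The hyperkalemia and arrhythmia records under Section 10.4 come after the harm.

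Third, the listed drugs differ. A reader might apply the potassium gaps to the whole list. Section 5.3 supports that argument only for drugs that alter potassium, which here means ACE inhibitors, ARBs and potassium-sparing diuretics. For dofetilide and methotrexate the gap is the missing switch prompt.

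**Conclusion.** The point holds as an omission in the visible text, not as a contradiction. A patient on co-trimoxazole who starts an ACE inhibitor, an ARB or a potassium-sparing diuretic after month 6 meets a scheduled potassium draw only at month 12 or 24, and none after that. The wait is 10 months in the month-14 example and up to 12 months on nominal visit dates. These are upper limits set by the schedule. The number of patients affected and the frequency of hyperkalemia among them cannot be derived from the documents.

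The conclusion assumes that Figure 1 contains no rule for newly started drugs. If it contains the switch rule, what remains is the missing potassium check and the medication update without a linked action.

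Two further inferences should be resisted. The omission does not bias the intention-to-treat comparison, because a change of agent within the antimicrobial arm leaves the assigned arm unchanged. Nor do the documents connect it with the early stop: the termination letter gives futility as the reason, reports no clear harm signal, and does not attribute the trends that it mentions to any drug combination. Because the trial has closed, the correction concerns the plan as written and any reuse of it.

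**What to change.** In Section 5, state that the listed-drug contraindications apply throughout co-trimoxazole therapy. Starting a listed drug then leads to a switch to doxycycline. If doxycycline is not possible, the investigator stops co-trimoxazole or, for potassium-raising drugs only, continues it with medical monitor input and a prompt local potassium test.

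As a backstop, add a flag for newly started listed drugs to the existing medication update. The Section 5 rule is the main remedy, because the flag gives an earlier usable prompt only for starts in months 12–18 and 24–30. If Figure 1 already contains the switch rule, repeat it in the text and add only the potassium check and the flag.

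The cost is a few sentences and one form item, with no new visits or contacts. The downside is an occasional local potassium test and some patients moving to doxycycline, which the protocol already allows. The primary model adjusts for the agent chosen before randomization, so a later switch does not change the analysis.
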